PROTOCOL: A Pilot Feasibility Study of Mindfulness-Oriented Recovery Enhancement with Pregnant Women with Opioid Use Disorder

Clinicaltrials.gov Identifier: NCT04824521

PRINCIPAL INVESTIGATOR: [name], School of Social Work, University of Montana, [contact]

DOCUMENT DATE: February 10, 2021

ATTACHMENTS:

Study Protocol

Data Collection Forms

Data Analysis Plan

STUDY PROTOCOL

OBJECTIVES

The primary objective of this study is to evaluate the feasibility and acceptability of a behavioral health intervention (Mindfulness-Oriented Recovery Enhancement) delivered via telehealth to pregnant women diagnosed with substance use disorder. We have been awarded a pilot grant through the University of Montana Center for Population Health Research to complete this research. We propose to recruit thirty pregnant women with substance use disorder from clinics, community organizations, and social media to participate in eight sessions of Mindfulness-Oriented Recovery Enhancement (MORE) via Zoom. We propose to conduct all study visits remotely via Zoom and are therefore asking to be able to consent participants remotely via Zoom as well.

Study visits would include (1) a pre-treatment assessment, (2) eight therapy sessions, (3) a mid-treatment assessment after four therapy sessions, and (4) a post-treatment assessment (see attached study timeline). During the pre-, mid-, and post-treatment assessment visits, participants will be asked to complete self-report measures (see attached), two structured clinical interviews (see attached) and a semi-structured qualitative interview (see attached). Participants will be asked to complete a brief questionnaire (see attached) before and after each session. The primary aims of this study are as follows.

Aim 1: To adapt the in-person MORE intervention for telehealth delivery.

Aim 2: To assess the overall feasibility and acceptability of this telehealth intervention.

Hypothesis: MORE delivered via telehealth will be both feasible and acceptable to participants.

DESIGN

In this study, we intend to recruit pregnant women with SUD. This study is specifically focused on evaluating the feasibility and acceptability of a behavioral health intervention for this population.

Women are eligible to be a part of the study if they (1) are 18 years old or older, (2) are able to speak and understand English, (3) are pregnant at the time of consent, (4) meet criteria for substance use disorder in the past year according to the Mini Neuropsychiatric Interview, and (5) have access to the internet and a smart device (though a tablet may be provided). Whether a participant meets criteria for SUD will not be known until the interview is conducted during the pre-assessment, but since we will be collecting sensitive information (i.e., symptoms of substance use disorder), we need to complete the informed consent process.

Participants will be recruited through two approaches. We will reach out to OBGYN providers, healthcare systems, pain management clinics, substance use treatment providers, health departments, community groups, and harm reduction services to advertise the study. These providers will be given flyers (see attached) to post and distribute to patients/clients. We will also advertise online through social media (see attached).

Potential participants will be instructed to call, text, or email the research team to participate in the study. To be a part of the study, women must

- (1) be 18 years old or older,
- (2) be able to speak and understand English,
- (3) be pregnant at the time of consent, and
- (4) meet criteria for substance use disorder in the past year according to the Mini Neuropsychiatric Interview (see attached)
- (5) have access to the internet and a smart device (a tablet may be provided).

Again, we will not know if the participant meets criteria for SUD until the interview is conducted during the pre-treatment assessment.

METHODS

Here we provide an outline of the study procedures for study participants.

1. Potential participants will contact study staff via phone, text, or email to enroll in the study.
2. Study staff will describe the study in detail, answer questions, and evaluate the potential participant for eligibility criteria.
3. If the potential participant is still interested in the study and meets all inclusion criteria, they will then set up a virtual appointment via Zoom to complete the pre-assessment visit.
4. During the pre-assessment visit, study staff will engage the participant in the informed consent process. After completing the informed consent process, participants will complete self-report measures, structured clinical interviews, and a semi-structured qualitative interview.
 - a. Participants will be asked to complete a battery of self-report measures including a demographic questionnaire and measures of parenting confidence and self-regulation (see below) via Qualtrics.
 - b. Study staff will conduct the Mini Neuropsychiatric Interview and the NIDA Modified Assist Tool (see attached).
 - c. Participants will engage in a semi-structured qualitative interview (see attached).
5. After completing the pre-treatment assessment via Zoom, study staff will schedule the first tele-health appointment.
6. Participants will complete four tele-health appointments via Zoom. These therapy sessions will last about one hour. Participants will complete a short questionnaire before and after the session (see attached). MORE sessions will begin with formal mindfulness practice followed by a debrief of the formal practice, psychoeducation, and an experimental exercise. Sessions will focus on the application of mindfulness, cognitive reappraisal, and savoring in managing pain, substance use, and stress related to parenting and relationships. All sessions will be audio-recorded, reviewed and scored using a fidelity measure by research assistants trained in MORE to ensure fidelity to the treatment.
7. Outside of therapy sessions, participants will be asked to complete fifteen minutes of homework per day during which they will practice mindfulness, reappraisal, and savoring techniques. Mindfulness techniques will include body scan (during which participants focus on sensations in their bodies), mindful breathing (during which participants focus on the sensation of breathing), and open monitoring mindfulness practice (during which the focus of attention is awareness itself and participants simply notice as thoughts and sensations arise). Mindful reappraisal is the application of mindfulness to restructure (or change) unhelpful thoughts to reduce negative feelings and unhelpful behavior. Savoring is the application of mindfulness to focus on and enhance pleasurable thoughts, feelings, and sensations.
8. After four therapy sessions, participants will complete a mid-treatment assessment via Zoom. Participants will complete the same self-report measures, structured clinical interviews, and semi-structured qualitative interview which they completed in the pre-treatment assessment.
9. Participants will complete the four remaining therapy sessions.
10. After completing the remaining therapy sessions, participants will complete a post-treatment assessment via Zoom. Participants will complete the same self-report measures, structured clinical interviews, and semi-structured qualitative interview which they completed in the pre-treatment and mid-treatment assessments.

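### All assessment visits and interviews are planned over Zoom, the channel under test, with no other mode described, so acceptability may look more favourable than it was

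*Protocol*

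**What the plan says.** Aim 2 in the protocol's OBJECTIVES is "To assess the overall feasibility and acceptability of this telehealth intervention". The recruitment target is stated without a derivation: "We propose to recruit thirty pregnant women with substance use disorder".

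The collection mode is set in the same section: "We propose to conduct all study visits remotely via Zoom". Remote consent is requested on that basis. The METHODS steps follow it:

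- Step 6, treatment: "Participants will complete four tele-health appointments via Zoom". Step 9 adds the four remaining sessions.
- Step 8, mid-treatment: "After four therapy sessions, participants will complete a mid-treatment assessment via Zoom".
- Step 10, post-treatment, once the remaining sessions are done: "participants will complete a post-treatment assessment via Zoom".

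Both assessments include the self-report measures, the structured interviews and the semi-structured interview. Step 4a puts the self-report battery in Qualtrics, as part of the Zoom assessment visit. The short questionnaire around each session has no stated channel. Telephone, text and email appear only at first contact (step 1): "Potential participants will contact study staff via phone, text, or email to enroll in the study". Internet access and a smart device are entry conditions, and a tablet may be supplied.

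The Statistical Analysis Plan gives means and standard deviations for the self-report measures and a thematic analysis of transcribed interviews. The visible text has no attendance, retention or missing-data analysis.

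**The concern.** The channel being evaluated is also the channel through which the evaluation is collected. A woman whose connection, device or private space fails for good loses the treatment and, with it, the only described route for saying why. The thematic analysis can use only interviews that took place. The pre-treatment interview cannot stand in for the later ones, because it comes before any session of MORE.

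Two things are at stake. First, acceptability evidence may lean towards the study's single hypothesis, because the women most likely to be missing are those for whom telehealth worked least well. Second, the reasons for technical failure may go unrecorded. A count of lost women does not separate a failed connection from childbirth, relapse or loss of interest, and that cause is useful both for judging telehealth (Aim 2) and for adapting MORE to it (Aim 1). An interview that was never held cannot be recovered at analysis; its absence can only be reported and bounded.

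**Working it through.** **1. Who is missed, reading the steps as written.**

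| Woman's experience | Reaches a mid- or post-treatment interview? |
|---|---|
| Intermittent Zoom trouble, still connects | Yes; she can describe the trouble there |
| Finishes the required sessions, then cannot connect for the assessment | No, because of the mode rule |
| Loses Zoom mid-course and stops sessions | Not at step 10 in any mode, because it follows completion; nor at step 8 if she stops before session four |

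The mode rule alone accounts for the second row. The third row combines the mode rule with the tie to session completion, so a telephone option placed only inside steps 8 and 10 would not reach it.

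**2. Size of the possible bias.** The documents give no expected loss, no acceptability rate and no feasibility threshold, so there is no planned figure to reproduce. Inputs:

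- N = 30, from OBJECTIVES.
- L = women lost to assessment because Zoom failed. Assumed 3, 6 or 9.
- a_c = proportion of assessed women who find telehealth acceptable. Assumed 90%.
- a_l = the same proportion among lost women. Unknown; varied from 0% to 90%.

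Formulas:

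- Observed = a_c
- All enrolled = [(N − L) × a_c + L × a_l] / N
- Overstatement = (L / N) × (a_c − a_l)
- Retention = (N − L) / N

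Example with L = 6 and a_l = 30%: (24 × 0.90 + 6 × 0.30) / 30 = (21.6 + 1.8) / 30 = 78%, against an observed 90%. The overstatement is 0.20 × 0.60 = 12 points.

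Figure for all 30 women, with the overstatement in points in brackets:

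| L | a_l = 0% | a_l = 30% | a_l = 60% | a_l = 90% | Retention |
|---|---|---|---|---|---|
| 3 | 81% (9) | 84% (6) | 87% (3) | 90% (0) | 90% |
| 6 | 72% (18) | 78% (12) | 84% (6) | 90% (0) | 80% |
| 9 | 63% (27) | 72% (18) | 81% (9) | 90% (0) | 70% |

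With a_c = 80%, the largest overstatements (a_l = 0%) are 8, 16 and 24 points. These are expected proportions, not counts of whole women.

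**3. Feasibility.** The retention column needs no report from the lost women. If all 30 are in the denominator, each technical loss lowers it, so it moves in the right direction without an interview.

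**The case against.** The strongest case on the other side has five parts.

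- **Not everything is collected over Zoom.** This is right: the self-report battery is in Qualtrics and the channel of the session questionnaire is not given. But the Qualtrics battery still needs internet and belongs to the Zoom visit. The content named for it in step 4a is demographics, parenting confidence and self-regulation, not views on telehealth.
- **A reader might infer that women with Zoom trouble cannot report it.** The documents do not support that. Anyone who still connects can raise it at a later interview, and a woman who attended all eight sessions despite trouble has shown that she can connect. The gap concerns lasting failure.
- **A reader might infer that telehealth will look more feasible than it was.** That does not follow. Staff see missed sessions and drop-out directly, and a rate over all enrolled women would show them. That the visible analysis plan defines no such rate is a separate gap.
- **The percentages are not the plan's.** This stands. No proportion finding telehealth acceptable is planned, the loss rates are assumed, and 9, 18 and 27 points are upper limits. The same reasoning applies to themes, which would be drawn from 27, 24 or 21 women instead of 30.
- **Silence is not prohibition.** METHODS is offered as an outline, and nothing bars a telephone call. A tablet may also solve a device problem, though not a connection or privacy problem. The attached timeline, interview guide and questionnaires are not in the available text and could hold another route or technology items. Still, the mode is stated in OBJECTIVES and in steps 8 and 10, and staff who follow it exactly have no instruction to use anything else.

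**Conclusion.** The point holds for acceptability and for reasons for technical failure. Every assessment visit and interview is planned over the channel under test, with no alternative described, so the evidence after treatment starts comes mainly from women who can still connect. The likely direction is favourable to telehealth, because lost women probably found it less acceptable.

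The size is unknown. On the assumed 90% among assessed women, it lies between 0 and 9, 18 or 27 points for 3, 6 or 9 women lost. It is zero if nobody is lost or if lost women hold the same views. It would be wrong to quote the upper limits as the expected effect, or to say that bias is certain.

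One remote channel is a defensible default for a 30-woman remote pilot. What is missing is a fallback, and adding one is a cheap improvement; the design does not need to change.

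**What to change.** In the OBJECTIVES sentence on study visits and in METHODS steps 8 and 10:

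1. Keep Zoom as the default. State that a woman who cannot or does not wish to use it may have the interviews by telephone, with the Qualtrics link sent by text or email.
2. Offer these assessments at the scheduled mid- and post-treatment times whether or not the sessions were completed. Without this, the telephone option misses women whose Zoom failed mid-course.
3. Record the mode of each assessment and, when it is not Zoom, the reason.

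In the Statistical Analysis Plan, report those reasons as a telehealth feasibility result, alongside attendance and retention with all enrolled women in the denominator.

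The cost is a few sentences in the protocol and the ethics-board wording, and some staff time to follow up women who stopped sessions. Staff already use telephone, text and email under step 1. The drawback is that a few interviews will lack video, so mode differs slightly between women. Because the interviews are verbal and analysed from transcripts, this should matter little.

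### Does requiring every inclusion criterion before the pre-assessment is booked, when substance use disorder is diagnosed only at that visit, affect who enters the study?

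*Protocol*

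**What the plan says.** The Protocol's Design section lists five inclusion criteria and introduces the second listing with "To be a part of the study, women must". The fourth is SUD in the past year, as determined by the Mini Neuropsychiatric Interview. The section is open about when this is established: "Whether a participant meets criteria for SUD will not be known until the interview is conducted during the pre-assessment". It gives the reason for taking consent first: "since we will be collecting sensitive information (i.e., symptoms of substance use disorder), we need to complete the informed consent process". Just before the Methods heading it repeats the point: "Again, we will not know if the participant meets criteria for SUD until the interview is conducted during the pre-treatment assessment".

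Methods then outlines the procedures in numbered steps. In step 2, staff evaluate eligibility at first contact. In step 3, a woman who is still interested and "meets all inclusion criteria, they will then set up a virtual appointment via Zoom to complete the pre-assessment visit". In step 4, consent is taken at that visit, and "After completing the informed consent process, participants will complete self-report measures, structured clinical interviews, and a semi-structured qualitative interview". Step 4b names the diagnostic instrument: "Study staff will conduct the Mini Neuropsychiatric Interview and the NIDA Modified Assist Tool (see attached". Step 5 schedules the first therapy session once the assessment is complete. Steps 6 to 10 cover the sessions and the later assessments and contain no further eligibility check.

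The Objectives section describes the target as thirty pregnant women with SUD, recruited to take part in eight sessions. The SAP plans means and standard deviations for the self-report measures and a thematic analysis of the interviews.

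**The concern.** Taken word for word, step 3 asks staff to confirm something they cannot yet know. It also seems to sit badly with the Protocol's own reason for taking consent before asking about symptoms of SUD, because someone trying to satisfy it literally would have to ask early.

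Step 5 appears to add to the problem. Its only stated condition is that the assessment has been completed, so the interview result is not tied to the decision to start therapy. If a woman without SUD went forward, she would receive an intervention meant for another population, and her data would enter the feasibility and acceptability results. The steps also do not say how a consented woman who fails the diagnostic criterion is to be counted. In a pilot whose purpose is feasibility, such counts are of interest.

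**Working it through.** The Protocol states no calculation on this point. The check is of the order of events and of who ends up in the study.

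**1. Order of events, read literally**

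- Booking (step 3) requires criteria 1 to 5.
- Criterion 4 requires the diagnostic interview (step 4b).
- The interview requires consent (step 4; Design gives the reason).
- Consent takes place at the visit that step 3 books.

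The chain closes on itself, so step 3 cannot be met to the letter for criterion 4. That is 1 of 5 criteria. Criterion 3, "be pregnant at the time of consent, and", is not a second case: pregnancy can be asked about at first contact, and the criterion already fixes the date on which it must hold.

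**2. Order of events, read with the Design section**

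Design says twice that criterion 4 is established at the pre-assessment, the second time directly above the numbered steps. On that reading, step 3 covers what can be checked at first contact (criteria 1, 2, 3 and 5) and step 4b supplies criterion 4. The circle disappears. No step tells staff to ask about SUD before consent, and both Design and step 4 put consent first.

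**3. Who proceeds past step 5**

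- The mandatory list makes criterion 4 a condition of being in the study.
- Methods is presented as an outline of what study participants do.
- A woman who fails criterion 4 is therefore not a participant for steps 5 to 10.

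The exposure that looks alarming is 8 sessions × about 1 hour = about 8 hours (taking the length given in step 6 to apply to the last four sessions as well), plus the mid- and post-treatment assessments. It arises only if staff disregard a stated mandatory criterion. It is the length of the course, not an estimate of any effect of the wording.

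**4. Who is counted**

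Let k be the number of consented women who do not meet criterion 4. The documents do not give k. Because the Objectives define the thirty as women with SUD:

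- present wording: women in the study = 30, women consented = 30 + k;
- step 3 limited to criteria 1, 2, 3 and 5: women in the study = 30, women consented = 30 + k.

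The difference is 0 for any k. The same women supply the means, standard deviations and interview transcripts.

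**The case for a change.** The strongest case for a change is that staff work from the numbered steps rather than from the preceding narrative. A step that cannot be carried out as written should be corrected, and the explanation in Design is exactly what shows the step to be wrong. Step 5 also remains silent on the interview result however step 3 is read. In addition, the self-report battery (4a) is listed before the diagnostic interview (4b), so a woman who turns out not to have SUD may already have provided questionnaire data, and the SAP does not say that her data are left out.

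Some of this stands. The wording of step 3 does conflict with Design, and a report that gave the number of consented women who failed criterion 4 would be more informative. But the mandatory list already decides whether such a woman is in the study, and an outline need not repeat an eligibility rule at each step. An analyst summarising a study of women with SUD would leave out someone found not to have it; that is the ordinary reading of the criterion and needs no new rule. The silence in step 5 is also weak evidence of a gap, because the timeline and forms that the Protocol cites as attachments are not in the supplied text and may hold the decision point.

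**Conclusion.** The inconsistency is real but clerical: one word in step 3 reaches 1 of 5 criteria that it should not, and the neighbouring text makes the intended meaning clear. The rule that keeps women without SUD out of the study is already stated, and the target of thirty is already defined in terms of SUD. Rewording would leave the enrolled population, the descriptive and thematic analyses and the feasibility conclusion unchanged, so no change to the plan follows.

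This rests on two assumptions: that staff read step 3 together with the eligibility text above it, and that no attachment says otherwise. It does not rest on any screen-failure rate, since the comparison gives the same result whatever that rate is. The missing count of consented women who fail criterion 4 is a reporting detail that the study team can supply from its own records.

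### No visible step assesses a woman who stops sessions early, so post-treatment interviews, followed as written, come only from completers

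*Protocol*

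**What the plan says.** The Protocol's Objectives give the relevant aim as "To assess the overall feasibility and acceptability of this telehealth intervention" and the recruitment target: "We propose to recruit thirty pregnant women with substance use disorder". They list three assessment visits (pre-, mid- and post-treatment), each with a semi-structured interview. No exit or withdrawal visit is listed.

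The Methods section then sets the order of events:

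- Step 8: "After four therapy sessions, participants will complete a mid-treatment assessment via Zoom".
- Step 9: "Participants will complete the four remaining therapy sessions".
- Step 10: "After completing the remaining therapy sessions, participants will complete a post-treatment assessment via Zoom". Its second sentence repeats the instruments "which they completed in the pre-treatment and mid-treatment assessments".

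Other data come from step 6 (a short questionnaire on either side of each session, and audio recording of sessions) and step 4a (a self-report battery). The named content of that battery is "a demographic questionnaire and measures of parenting confidence and self-regulation". Step 4a introduces this list as partial and points to further detail that is not in the visible text.

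The visible SAP plans means and standard deviations for the self-report measures and a thematic analysis of the interview recordings. It does not mention women who stop, missing interviews or reporting by completion status.

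**The concern.** Steps 8 to 10 follow one course: a woman reaches session 4, is assessed, finishes the remaining sessions and is assessed again. Step 10 also presumes that she already has a mid-treatment assessment. A woman who leaves that course has no described next step.

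This matters because stopping is itself evidence about feasibility and acceptability. If women who stop are not invited to an interview, the post-treatment accounts come from the women who stayed. No visible step then records systematically why the others left. The hypothesis is that MORE by telehealth is both feasible and acceptable, and the women most likely to qualify that answer would have the least opportunity to do so. Their reasons may be hard to recover if nobody asks at or near the time they stop.

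**Working it through.** The plan states no dropout rate, acceptability threshold or derivation of the sample size, so it has no figure to reproduce. The check is a reading of the steps, followed by a count.

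**Reading.** What each woman gives after sessions begin, if the steps are followed literally:

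| Course | Mid-treatment interview | Post-treatment interview |
|---|---|---|
| Completes all 8 sessions | yes | yes |
| Stops in sessions 5–8 | yes, before she stops | no |
| Stops before completing session 4 | no | no |

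An early stopper is left with the pre-treatment interview only. Steps 4 and 5 place that interview before the first session is scheduled, so it cannot report experience of MORE. A later stopper's mid-treatment interview can report her experience of the first four sessions, but not why she later stopped.

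**Count from the documents.** With 30 women and 3 interviews each, 30 × 3 = 90 are planned. Of these, 30 × 2 = 60 fall after sessions begin. This takes all 30 as eligible and starting sessions. The Protocol confirms substance use disorder only after consent, so the number who start may be smaller.

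**Illustration.** Let m women stop, e of them before completing session 4. Each stopper loses the post-treatment interview and each early stopper also loses the mid-treatment one:

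interviews not held = m + e; post-treatment interviews left = 30 − m.

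Assumed inputs: m = 6 or 12, with e between one third and two thirds of m.

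- m = 6, e = 2 to 4: 6 + 2 = 8 to 6 + 4 = 10 of 60 not held; 30 − 6 = 24 post-treatment interviews left.
- m = 12, e = 4 to 8: 12 + 4 = 16 to 12 + 8 = 20 of 60 not held; 30 − 12 = 18 left.
- Women with no interview after starting MORE: e = 2 to 4, or 4 to 8.
- Exit interviews gained if one third to two thirds of stoppers accept (also assumed): 2 to 4 for m = 6, or 4 to 8 for m = 12.

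**Bias.** If acceptability were summarised as a proportion, which the visible plan does not do, a completers-only figure would differ from the figure for all women by d × (p_c − p_s). Here d is the share who stop, and p_c and p_s are the proportions of completers and stoppers who find MORE acceptable. With p_c assumed at 90% and d = 6/30 = 20%, the difference is 0, 6 or 12 points for p_s = 90%, 60% or 30%. With d = 12/30 = 40% it is 0, 12 or 24 points. The documents supply none of these inputs, so the range of 0 to 24 points reflects the assumptions only.

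**The case against.** The strongest reply is that the steps give timing, not eligibility. The Methods section calls itself an outline, and the Objectives list the post-treatment assessment without making completion a condition. That stands: a reader might infer that women who stop are excluded, and the documents do not say so. They are silent, which leaves the invitation to staff discretion.

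Three further inferences go too far:

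- *That all interview themes come from completers.* Step 8 requires only four sessions, so later stoppers contribute a mid-treatment interview. The SAP's thematic analysis covers the interview recordings generally and defines no separate post-treatment set.
- *That the interviews are the only measure of acceptability.* The battery in step 4a is only partly listed, and the session questionnaires and the interview guide are not shown. An acceptability scale may be among the unseen measures. It also cannot be confirmed that the interview asks about acceptability, since the same interview is planned before any session takes place.
- *That a bias has been shown.* No dropout rate is given, and the counts above rest on assumed inputs.

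The study timeline is an unseen attachment and part of the SAP is not shown. Either may already provide for women who stop. What remains is that no visible step provides an assessment for them, although the instrument and the Zoom format already exist.

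**Conclusion.** The point holds in a limited form. Followed as written, the steps give post-treatment interviews from completers only, no on- or post-treatment interview from a woman who stops before completing session 4, and no interview after stopping from a woman who stops in sessions 5 to 8. Attendance, the session questionnaires and the mid-treatment interviews still inform Aim 2, so the aim is weakened rather than left without data from women who stop.

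The size of any bias cannot be derived. Under the assumed 6 to 12 stoppers of 30, the loss is 8 to 20 of 60 interviews (8/60 = 13% to 20/60 = 33%). This rests on a literal reading of an outline, on all 30 women starting sessions, and on the assumed early/late split. It is worth changing because it affects what is collected on the main question and the remedy is cheap. Confidence is moderate, because of the material that cannot be seen.

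**What to change.** Keep the session-based timing for women who continue. Then:

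- **Step 10.** State that every eligible woman who has started sessions and stops early, and has not withdrawn consent for further contact, is invited to the existing post-treatment Zoom assessment. At a minimum, invite her to its semi-structured interview, with a question on her reasons for stopping. Fix the timing in the text: either when she stops or when her sessions would have ended. This wording separates stopping sessions from withdrawing from the study, and leaves out women found ineligible after consent.
- **SAP.** Report how many completers and non-completers were interviewed out of all who started. Describe non-completers' themes alongside completers' themes, noting that numbers may be small (as few as 2 exit interviews in the illustration).
- **If already covered.** If the attached timeline or the part of the SAP not shown makes this provision, cite it in steps 8 and 10.

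The cost is a short addition to step 10, one interview question and one reporting line. An exit interview replaces the woman's own planned post-treatment interview, so the total stays within 90. In the illustration this means 6 to 12 invitations, fewer if some women withdraw consent to contact, and 2 to 8 interviews with existing instruments. The downside is modest contact effort, and some women will decline, so coverage of non-completers will stay partial.
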